7.7.2 Over the whole trial

Similar to the 52 week period, exposure data over the whole trial will be summarised on both co-primary populations, as well as the complementary patient population.

7.8 SAFETY ANALYSIS

All safety analyses will be performed on the treated set. Particular focus will be given to evaluations over the 52 week period (Part A of the study).

7.8.1 Adverse events

Unless otherwise specified, the analyses of adverse events will be descriptive in nature. All analyses of AEs will be based on the number of patients with AEs and NOT on the number of AEs.

For analysis multiple AE occurrence data on the eCRF will be collapsed into an AE provided that all of the following applies:

- All AE attributes are identical (LLT, intensity, action taken, therapy required, seriousness, reason for seriousness, relationship, outcome, AESI; CTCAE if applicable)
- The occurrences were time-overlapping or time-adjacent (time-adjacency of 2 occurrences is given if the second occurrence started on the same day or on the day after the end of the first occurrence).

For further details on summarization of AE data, please refer to (7, 8).

The analysis of adverse events will be based on the concept of treatment emergent adverse events. That means that all adverse events occurring between first drug intake until last drug intake + 28 days (and + 7 days as sensitivity analysis) will be assigned to the randomised treatment.

All adverse events occurring before first drug intake will be assigned either to 'screening' or 'post-randomisation' (for listings only).

All adverse events occurring after last drug intake + 28 days (and + 7 days as sensitivity analysis) will be assigned to 'post-treatment' or 'follow-up' or 'post-study' (for listings only). All adverse events occurring between the start of an interruption of trial medication and the

end of interruption of trial medication will be assigned to 'off-treatment' period in the listings. For details on the treatment definition, see [Section 6.1](#).

According to ICH E3 ([10](#)), AEs classified as 'other significant' need to be reported and will include those non-serious and non-significant adverse events with (i) 'action taken = discontinuation' or 'action taken = reduced', or (ii) marked haematological and other lab abnormalities or lead to significant concomitant therapy as identified by the Clinical Monitor/Investigator at a Medical Quality Review Meeting.

Adverse events related to gastrointestinal perforation and hepatic injury will be considered as protocol-specified AEs of special interest (AESIs), and ticked as such in the eCRF.

Table 7.8.1: 1 Protocol-specified AESI

Protocol-specified AESI	AE type
Gastrointestinal perforation	AEs established for other tyrosine kinase inhibitors as possible adverse reactions
Hepatic injury	Other AEs of interest

Further adverse event groupings by safety topic have been defined outside the trial protocol, which will be continuously updated at project level ([18](#)). These safety topics are deemed of particular importance, and these definitions can be based on selection of coded terms based on MedDRA. The latest approved version of the project level overview archived prior to either DBL will be used in the corresponding CTR.

7.8.1.1 Over 52 weeks

An overall summary of adverse events having occurred over the first 52 weeks will be presented on the co-primary populations, as well as on the complementary population,, including all AEs occurring between first drug intake until:

- last drug intake + 28 days (and + 7 days as sensitivity analysis) for patients who prematurely discontinued the study medication before 52 weeks (i.e. 372 days after first trial drug intake)
- week 52 for patients who did not prematurely discontinue the study medication before 52 weeks

The frequency of patients with adverse events in the co-primary populations, as well as in the complementary population, will be summarised by treatment, primary system organ class and preferred term. Separate tables will be provided for patients with other significant adverse events according to ICH E3 ([10](#)) and for patients with protocol-specified adverse events of special interest (as ticked in the AE page of the eCRF [gastrointestinal perforation and hepatic injury]). Displays will also be provided for patients with any adverse events, severe adverse events and also serious adverse events, for patients with adverse events occurring with an incidence in preferred term greater than 5% (in at least one treatment arm), for patients with adverse events leading to permanent dose reduction, for patients with adverse events leading to treatment discontinuation, for patients with investigator defined drug-related adverse events, for patients with drug-related serious adverse events (in co-primary populations only),

and for patients with adverse events leading to death. Further, the frequency of patients with adverse event by system will be provided.

The frequency of patients with adverse events will also be provided by system, safety topic, subcategory (if applicable) and preferred term, with groupings as defined in (18). These displays will focus on patients with any adverse events, patients with serious adverse events and patients with related adverse events.

Additional outputs will be created for the subgroups depicted in [Section 6.4](#) focusing on the overall summary of adverse events, patients with adverse events occurring with an incidence in preferred term greater than 5% (in at least one treatment arm), patients with serious adverse events and patients with related adverse events. An exact overview can be found in [Table 7.4.3: 1](#).

The system organ classes (SOC) will be sorted according to the standard sort order specified by EMA, preferred terms will be sorted by frequency in Nintedanib treatment arm (within SOC).

7.8.1.2 Over the whole trial

Time at risk analyses of AEs will be presented and incidence rates per 100 patient years will be calculated based on the first onset of an AE (see [Section 7.8.1.5](#) for details). An overall summary of adverse events over the whole trial will be presented on the co-primary populations.

The frequency of patients with adverse events in the co-primary populations, as well as in the complementary population, will be summarised by treatment, primary system organ class and preferred term. Separate tables will be provided for patients with other significant adverse events according to ICH E3 (10) and for patients with protocol-specified adverse events of special interest (as ticked in the AE page of the eCRF [gastrointestinal perforation and hepatic injury]). Displays will also be provided for patients with any adverse events, severe adverse events and also serious adverse events, for patients with adverse events occurring with an incidence in preferred term greater than 5% (in at least one treatment arm), for patients with adverse events leading to permanent dose reduction, for patients with adverse events leading to treatment discontinuation, for patients with investigator defined drug-related adverse events, for patients with drug-related serious adverse events (in co-primary populations only), and for patients with adverse events leading to death. Further, the frequency of patients with adverse event by system will be provided.

The overall summary of adverse events and the frequency of patients with adverse events (by treatment, primary system organ class and preferred term) will also be presented on patients with “other HRCT fibrotic patterns”. Separate tables will be provided for patients with protocol-specified adverse events of special interest, for patients with serious adverse events, for patients with adverse events leading to permanent dose reduction, for patients with adverse events leading to treatment discontinuation, and for patients with adverse events leading to death.

Displays by safety topic will also be created over the whole trial, as well as outputs for the subgroups.

7.8.1.3 Adjudicated adverse events

An independent adjudication committee will review all fatal cases and adjudicate cause of death to respiratory, cardiovascular or other. The adjudication committee will also review all AEs categorised as MACE according to the definition in the adjudication charter.

In addition to standard safety analyses, the frequency of patients with AEs leading to death will be summarised by treatment, adjudicated cause of death (Cardiovascular, Respiratory or Other), and PT.

The frequency of patients with AEs categorised as MACE (that is all AEs categorised as MACE and therefore sent for adjudication) will be summarised by treatment and outcome of adjudication (adjudicated as MACE or adjudicated as not MACE). The frequency of patients with AEs adjudicated as MACE will also be summarised by treatment and PT.

7.8.1.4 Adverse events with additional information collection

Diarrhoea, bleeding and ILD are AEs with additional AE-specific information collected on the eCRF. These are investigator reported on the eCRF and will be identified using this information for this analysis. That is if the diarrhoea information has been completed for an adverse event then the adverse event will be considered as diarrhoea for this analysis regardless of subsequent MedDRA coding of the verbatim term. Likewise, if the bleeding information has been completed for an adverse event then the adverse event will be considered as bleeding for this analysis regardless of subsequent MedDRA coding of the verbatim term. The same applies to ILD.

The frequency of patients with AEs with additional information collection will be summarised by treatment, primary SOC and PT separately for diarrhoea, bleeding and ILD. The additional information collected will also be summarised at the AE level rather than at the patient level separately for diarrhoea, bleeding and ILD. For the time to first onset of diarrhoea, bleeding or ILD, respectively, Kaplan-Meier plots by treatment will be created. The same censoring rules as for time to first liver enzyme elevation will be used. See [Table 5.4.4: 1](#) and [Table 5.4.4: 2](#) for details. Please note that these evaluations are prepared for the co-primary populations, as well as in the complementary population, and covering both analysis periods “over 52 weeks” and “over the whole trial”.

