During the nintedanib trials 1199.32 and 1199.34, the most commonly reported adverse events ($\geq 10\%$ and ≥ 1.5 times placebo) experienced with nintedanib were diarrhoea (nintedanib 62.4% vs placebo 18.4%), nausea (24.5% vs 6.6%), abdominal pain (15.0% vs 6.1%), vomiting (11.6% vs 2.6%) and decreased appetite (10.7% vs 5.7%). Most of these AEs were of mild or moderate intensity, reported as non-serious, and were managed by symptomatic treatment and/or temporary interruption and/or reduction of the nintedanib

dosage. 19% of patients treated with nintedanib had an adverse event leading to treatment discontinuation (compared to 13% in the placebo treatment group). The most commonly reported adverse events ($\geq 1\%$ and more than for placebo) leading to nintedanib discontinuation were diarrhoea (4.4%), nausea (2.0%) and decreased appetite (1.4%).

Liver enzyme elevations (AST and/or ALT $\geq 3 \times$ ULN) were experienced by 5.0% of patients treated with nintedanib in the phase III trials (versus 0.7% of patients treated with placebo).

Arterial thromboembolic events were infrequently reported: in 0.7% of patients in the placebo and 2.5% in the nintedanib treated group. While adverse events reflecting ischemic heart disease were overall balanced between the nintedanib and placebo groups, within this group of terms a higher percentage of patients experienced myocardial infarctions in the nintedanib group (1.6%) compared to the placebo group (0.5%).

For further details refer to the current version of the Investigators Brochure

In conclusion: the most frequent AEs were gastrointestinal events which were manageable by the proposed dose regimen that includes dose reduction and dosing interruption. This dosing regimen was also effective in the management of liver enzyme and bilirubin elevations that are associated with nintedanib treatment.

Overall, the evidence available from the clinical development programme demonstrates a favourable benefit-risk balance for nintedanib in the treatment of patients with IPF.

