Potential DILI cases are defined as AESIs, and are reported and processed following the SAE process on the respective SAE form.

In case of clinical symptoms of hepatic injury (icterus, unexplained encephalopathy, unexplained coagulopathy, right upper quadrant abdominal pain, etc.) without lab results (ALT, AST and total bilirubin) available, the Investigator should make sure these parameters are analysed, if necessary in an unscheduled blood test. Should the results meet the criteria of hepatic injury alert, the procedures described in the DILI checklist should be followed.

Intensity of AEs

The intensity of the AE should be judged based on the following:

Mild: Awareness of sign(s) or symptom(s) that is/are easily tolerated

Moderate: Enough discomfort to cause interference with usual activity

Severe: Incapacitating or causing inability to work or to perform usual activities

In addition the intensity of diarrhoea adverse events should be classified and recorded in the eCRF according to the Common Terminology Criteria for adverse events (CTCAE) version 4 ([R10-4848](#), Table 5.3.6.1:1).

Table 5.3.6.1:1 CTCAE Categorization for diarrhoea

CTCAE Grade	Diarrhoea
1	Increase of <4 stools per day over baseline
2	Increase of 4 to 6 stools per day over baseline
3	Increase of ≥ 7 stools per day over baseline; incontinence
4	Life threatening consequences
5	Death

Causal relationship of AEs

The definition of an adverse reaction implies at least a reasonable possibility of a causal relationship between a suspected medicinal product and an adverse event. An adverse reaction, in contrast to an adverse event, is characterized by the fact that a causal relationship between a medicinal product and an occurrence is suspected.

Medical judgment should be used to determine the relationship, considering all relevant factors, including pattern of reaction, temporal relationship, de-challenge or re-challenge,

confounding factors such as concomitant medication, concomitant diseases and relevant history.

Arguments that may suggest that there is a reasonable possibility of a causal relationship could be:

- The event is consistent with the known pharmacology of the drug
- The event is known to be caused by or attributed to the drug class.
- A plausible time to onset of the event relative to the time of drug exposure.
- Evidence that the event is reproducible when the drug is re-introduced.

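### CTCAE grade of diarrhoea is to be summarised by AE record rather than by patient, and no visible planned output gives the share of treated patients per arm by worst grade

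*SAP*

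**What the plan says.** - **Collection.** Protocol 5.3.6.1 defines a general mild/moderate/severe scale for all events and then adds a grade for diarrhoea: "In addition the intensity of diarrhoea adverse events should be classified and recorded in the eCRF according to the Common Terminology Criteria" (version 4, grades 1 to 5). Protocol 5.3.7 has further diarrhoea details entered in the eCRF, on top of standard reporting.
- **General counting rule.** SAP 7.8.1 says all AE analyses are "based on the number of patients with AEs and NOT on the number of AEs". It merges overlapping or adjacent records only when every listed attribute matches. The list includes intensity, action taken and CTCAE grade.
- **Diarrhoea section.** SAP 7.8.1.4 first plans patient counts without grade: "The frequency of patients with AEs with additional information collection will be summarised by treatment, primary SOC and PT". It then changes the unit: "The additional information collected will also be summarised at the AE level rather than at the patient level". It adds Kaplan-Meier plots of time to first onset. It gives no reason for the change of unit, no denominator, and no list of the items that make up the additional information.
- **Related patient-level displays.** SAP 7.8.1.1 and 7.8.1.2 plan displays of patients with severe events, serious events, and events leading to permanent dose reduction, discontinuation or death. Protocol 7.3.4 tabulates severity by system organ class and preferred term. SAP 7.8.1.5 adds exposure-adjusted incidence rates, without grade.

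**The concern.** Diarrhoea was the most frequent adverse event with nintedanib in the IPF trials (62.4% against 18.4% on placebo, protocol 1.2), and the protocol has its CTCAE grade collected as a separate item. The quantity a benefit-risk reader wants is the proportion of treated patients in each arm whose worst diarrhoea reached a given grade, grade 3 or above in particular. A summary whose unit is the AE record does not supply it. A patient with several records counts several times. If the percentage is taken over diarrhoea records, the table also describes only events in patients who had diarrhoea, which is itself an outcome of treatment. At stake is whether the report shows the graded risk of this harm per patient in each arm. No efficacy conclusion is affected.

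**Working it through.** The plan states no figure on this point, so there is none to reproduce. The check has two parts.

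**1. Does any planned output give worst CTCAE diarrhoea grade per patient?**

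- SAP 7.8.1.4, patient counts: patients are the unit, but there is no grade.
- SAP 7.8.1.4, additional information: grade by reasonable inference, but AE records are the unit.
- SAP 7.8.1.1 and 7.8.1.2, severe events: patients are the unit, on the general scale. Severe there means "Incapacitating or causing inability to work or to perform usual activities", a functional definition. CTCAE grade 3 is an increase of at least 7 "stools per day over baseline; incontinence". The case definition differs too: these displays go by coded preferred term, while 7.8.1.4 takes any event with the diarrhoea information completed, however it was coded.
- Serious, dose-reduction, discontinuation and death displays: patients are the unit, and the classification is by consequence, not grade.
- SAP 7.8.1.5: rates by preferred term and safety topic, without grade.

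None gives it.

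**2. What can the AE-level summary show instead?**

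Inputs from the documents: 300 patients per arm (protocol 3.1); diarrhoea in 62.4% and 18.4% (protocol 1.2, IPF trials). Patients with diarrhoea: 0.624 × 300 = 187 and 0.184 × 300 = 55.

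Assumed inputs, in neither document: records per patient with diarrhoea; patients with grade 3 or above; and exactly one such record for each of those patients.

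Patient-level share = patients with grade ≥3 / 300. Record-level share = grade ≥3 records / (patients with diarrhoea × records per patient). All comparisons are nintedanib against placebo.

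| Records per patient | Patients with grade ≥3 | % of patients | % of diarrhoea records | Order of arms |
|---|---|---|---|---|
| 1.0 vs 1.0 | 9 vs 3 | 3.0 vs 1.0 | 9/187 = 4.8 vs 3/55 = 5.5 | differs |
| 1.0 vs 1.0 | 15 vs 3 | 5.0 vs 1.0 | 15/187 = 8.0 vs 3/55 = 5.5 | same |
| 1.5 vs 1.2 | 15 vs 3 | 5.0 vs 1.0 | 15/280.5 = 5.3 vs 3/66 = 4.5 | same |
| 2.0 vs 1.2 | 15 vs 3 | 5.0 vs 1.0 | 15/374 = 4.0 vs 3/66 = 4.5 | differs |
| 3.0 vs 1.2 | 15 vs 3 | 5.0 vs 1.0 | 15/561 = 2.7 vs 3/66 = 4.5 | differs |
| 2.0 vs 1.2 | 30 vs 3 | 10.0 vs 1.0 | 30/374 = 8.0 vs 3/66 = 4.5 | same |

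Under these assumptions the order differs when the patient-level risk ratio for grade ≥3 is above 1 but below the ratio of total diarrhoea records. That ratio is 187/55 = 3.4 with one record per patient in both arms, 280.5/66 = 4.25 with 1.5 vs 1.2, 374/66 = 5.7 with 2.0 vs 1.2, and 561/66 = 8.5 with 3.0 vs 1.2. Over a grid of 4 × 3 × 4 × 3 = 144 combinations (1, 1.5, 2 or 3 vs 1, 1.2 or 1.5 records per patient; 9, 15, 21 or 30 vs 2, 3 or 6 patients with grade ≥3), the order differed in 65. That count describes the grid and is not a probability.

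**The other denominator.** The introduction to SAP 7 takes percentages relative to the treatment group, meaning all patients in the set, unless otherwise specified. With 300 as denominator and one grade ≥3 record per affected patient, the record-level and patient-level figures coincide by construction, so none of the 144 combinations changes order. The unit still fails in two ways. At 2.0 records per patient, all nintedanib diarrhoea records over patients is 374/300 = 125%. If each of 15 patients had two grade ≥3 records, the table would show 30/300 = 10.0% where 5.0% of patients were affected.

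**The case against.** The case against is substantial on several points.

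- **Severity per patient is largely covered.** Readers will see severe and serious diarrhoea, and diarrhoea leading to dose reduction or discontinuation, counted by patient and arm. The AE-level summary is an addition to the patient counts. This stands as mitigation. It does not close the gap, because scale and case definition differ.
- **A change in the order of the arms needs an unstated denominator.** A reader might infer that the AE-level table will point the wrong way. The documents do not support that. SAP 7.8.1.4 does not say that percentages are taken over records, the SAP default is patients in the arm, and on that default the tested combinations keep their order. Even over records, most combinations keep it.
- **The inputs are assumed.** Only the two incidences and the arm size come from the documents, and the incidences come from IPF. Neither document says whether sites open a new record when the grade changes, so how far episodes split is unknown. If severe episodes split as much as mild ones, the dilution shrinks.
- **Other sources may hold the table.** A reader might infer that the trial never reports graded diarrhoea per patient. SAP 7.8.1 also refers to sponsor standards and a project-level safety-topic file that are not part of these documents, so the statement has to be limited to what is visible.
- **AE analyses are descriptive.** True, but a descriptive table still needs a unit that answers the question.

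That the additional information includes CTCAE grade is an inference from protocol 5.3.6.1 and 5.3.7 and from the attribute list in SAP 7.8.1. If it does not, CTCAE grade has no named summary at all.

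**Conclusion.** The point holds in a limited form. The unit of analysis in SAP 7.8.1.4 departs from the SAP's own general rule without explanation, and no visible output reports treated patients per arm by worst CTCAE diarrhoea grade. An episode entered as several records is counted several times, and the AE-level summary does not give patient risk under either denominator. The size cannot be fixed from the documents. With 15 vs 3 patients at grade ≥3 (5.0% vs 1.0%), the share of records on nintedanib runs from 5.3% to 2.7% at 1.5 to 3.0 records per patient, against 4.5% on placebo at 1.2. The order of the arms is therefore kept at the low end and changed at the high end. This rests on assumed grades and record counts, one grade ≥3 record per affected patient, and a records denominator that the SAP does not state. The conclusion about the missing patient-level table needs none of these assumptions.

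**What to change.** In SAP 7.8.1.4, add a table of patients by worst on-treatment CTCAE grade of diarrhoea, with a line for grade 3 or above, by treatment. Use all treated patients as denominator, and produce it over 52 weeks and over the whole trial. Take cases by the definition already in that section (diarrhoea information completed in the eCRF). Keep the AE-level summary as supportive, state its denominator, and say that CTCAE grade is among the items summarised.

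Cost: one extra descriptive table per analysis period, from data already collected. No dosing or other clinical rule is touched. It is a cheap improvement.
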